7.3 Expedited Adverse Event Reporting

7.3.1 Investigators **must** report to the Overall PI any SAE that occurs after the initial dose of study treatment, during treatment, or within 30 days of the last dose of treatment.

7.3.2 DF/HCC Expedited Reporting Guidelines

Investigative sites within DF/HCC will report AEs directly to the DFCI Office for Human Research Studies (OHRS) per the DFCI IRB reporting policy.

7.3.3 Protocol-Specific Expedited Adverse Event Reporting Exclusions

For this protocol only, the AEs/grades listed below do not require expedited reporting to the Overall PI or the DFCI IRB. However, they still must be reported through the routine reporting mechanism (i.e. case report form).

CTCAE SOC	Adverse Event	Grade	Resulting in Hospitalization/ Prolongation of Hospitalization	Attribution	Comments
Investigations	Neutrophil count decreased	4	No	Definite, probable, or possible	Only applies if the AE does not involve a hospitalization/prolongation of hospitalization (otherwise needs to be reported)
Investigations	White blood cell decreased	4	No	Definite, probable, or possible	Only applies if the AE does not involve a hospitalization/prolongation of hospitalization (otherwise needs to be reported)
Investigations	Platelet count decreased	4	No	Definite, probable, or possible	Only applies if the AE does not involve a hospitalization/prolongation

					of hospitalization (otherwise needs to be reported)
Investigations	Lymphocyte count decreased	4	No	Definite, probable, or possible	Only applies if the AE does not involve a hospitalization/prolongation of hospitalization (otherwise needs to be reported)

7.4 Expedited Reporting to the Food and Drug Administration (FDA)

The Overall PI, as study sponsor, will be responsible for all communications with the FDA. The Overall PI will report to the FDA, regardless of the site of occurrence, any SAE that meets the FDA’s criteria for expedited reporting following the reporting requirements and timelines set by the FDA.

7.5 Expedited Reporting to Hospital Risk Management

Participating investigators will report to their local Risk Management office any participant safety reports or sentinel events that require reporting according to institutional policy.

7.6 Routine Adverse Event Reporting

[figure not shown]
All Adverse Events **must** be reported in routine study data submissions to the Overall PI on the toxicity case report forms. **AEs reported through expedited processes (e.g., reported to the IRB, FDA, etc.) must also be reported in routine study data submissions.**

8. PHARMACEUTICAL INFORMATION

A list of the AEs and potential risks associated with the investigational agent administered in this study can be found in **Section 6.1**.

8.1 LY2606368/Prexasertib

8.1.1 Description

Structure of LY2606368 mesylate monohydrate (LSN2940930).

Chemical name: 2-Pyrazinecarbonitrile, 5-[[5-[2-(3-aminopropoxy)-6-methoxyphenyl]-1H-pyrazol-3-yl]amino] monomesylate monohydrate

Molecular formula: C₁₉H₂₅N₇O₆S

Molecular weight: 479.51

pKa: 10.0 (basic) and 3.23 (basic)

pH: 5.51 (water slurry 10 mg/mL)

Specific Rotation, [α]²⁰_D: Not applicable, achiral

pI: Not applicable

Solubility: Methanol 8.44 mg/mL (slightly soluble)

8.1.2 Form

Prexasertib (LY2606368) for injection is supplied for clinical trial use as a lyophilized, yellow to white solid, in glass vials, and is composed of prexasertib mesylate monohydrate and the inactive ingredient sulfobutylether-β-cyclodextrin (Captisol). The drug product is available in two vial strengths containing either 20 mg or 40 mg of the base compound prexasertib. The 40 mg strength vial contains a 3% excess whereas the 20 mg strength vial contains a 5% excess to facilitate the withdrawal of the label amount (40 mg/vial and 20 mg/vial, respectively) for application with an appropriate device, such as an infusion set.

Reconstituting the 40 or 20 mg vial contents with 19 mL or 10 mL of water, respectively, yields a clear yellow solution with a concentration of 2 mg/mL of prexasertib, pH 4 to 6, and an osmotic pressure ratio of 344 mOsm.

The reconstituted solution may be diluted with dextrose 5% injection (D5W) prior to administration.

8.1.3 Storage and Stability

The drug product is stable when stored at room temperature at 10°C - 30°C (50°F to 86°F). Do not freeze or refrigerate prexasertib (LY2606368).

The reconstituted formulation is stable for at least 24 hours at room temperature; however, since the reconstituted drug product does not contain a preservative, the unused solution must be discarded after 6 hours. The infusion should be completed within 4 hours of priming the infusion set.

The investigator or pharmacist will ensure that all investigational products are stored in a secure area, under recommended storage conditions and in accordance with applicable regulatory requirements. The site should monitor the minimum and maximum temperature and maintain temperature logs to confirm the correct storage of all investigational products used in the trial.

8.1.4 Compatibility

Prexasertib (LY2606368) is incompatible with solutions containing saline or Lactated Ringer's and must not be mixed or administered simultaneously with other drugs through the same infusion line.

8.1.5 Handling

Qualified personnel, familiar with procedures that minimize undue exposure to themselves and the environment, should undertake the preparation, handling, and safe disposal of the chemotherapeutic agent in a self-contained and protective environment.

8.1.6 Availability

Prexasertib (LY2606368) is an investigational agent that will be supplied by Eli Lilly and Company.

8.1.7 Preparation

Prexasertib (LY2606368) diluted in D5W is compatible with standard IV solution bags constructed of polyolefin or polyvinyl chloride (PVC). Contact with PVC bags should be limited to not more than 6 hours. Administration sets constructed of PVC (with DEHP or TOTM), polyethylene-lined (paclitaxel) may be used. Administration sets with integrated filters or filter extension sets **MUST** be used for all patients. Compatibility with filters fabricated from polyether sulfone has been demonstrated.

Table 9 illustrates the compatible materials for prexasertib administration.

Table 9: Compatible Materials for Prexasertib Administration

Vendor	Description	Item Tested	Primary Contact Surface	Comparable Administration Supplies
Baxter	IntraVia Empty IV Infusion Bag, 250 mL	2B8012	Polyolefin Minimal PVC (with DEHP) Contact	Polyolefin, Excel (BBraun)
Baxter	Paclitaxel IV Infusion Set with 0.2 µm Filter	2C7557	Polyolefin Lined PVC without DEHP Polyether sulfone filter	Alaris, 10011433 Alaris, 10015048 Baxter Extension Set 0.2micron Filter (1C8363) Kawasumi, IV Add On Extension, IV-F02Y
Baxter	Interlink Infusion Set	2C6419S	PVC and DEHP	Alaris 72013E
BBraun	IV Administration Set	V1415-15	PVC and TOTM	None Identified
Baxter	5% Dextrose, USP, 250 mL	2B0062	PVC and DEHP	None Identified

8.1.7.1 Prexasertib 20 mg:

Prexasertib for injection, 20 mg: Reconstituted by adding 10 mL of water for injection and shaking. The resulting solution contains 2 mg/mL of prexasertib for injection.

Multiple vials of prexasertib will be required to prepare most dosage strengths. Obtain the number of vials needed to prepare the desired dose and reconstitute each vial with 10 mL of water for injection.

Transfer the total volume of solution required into an IV bag for subsequent dilution. Reconstituted drug product from the vials should be diluted with dextrose 5% injection (D5W) to a final volume of no more than 250 mL. If less than 250 mL is used, the concentration of prexasertib must be maintained within a range of 0.08 mg/mL - 1.6 mg/mL of prexasertib.

Reconstituted or diluted prexasertib should NOT be used if it appears turbid or contains foreign particles.

8.1.7.2 Prexasertib 40 mg:

Prexasertib for injection, 40 mg: Reconstituted by adding 19 mL of water for injection and shaking. The resulting solution contains 2 mg/mL of prexasertib for injection.

Multiple vials of prexasertib will be required to prepare most dosage strengths. Obtain the number of vials needed to prepare the desired dose and reconstitute each vial with 19 mL of water for injection.

Transfer the total volume of solution required into an IV bag for subsequent dilution. Reconstituted drug product from the vials should be diluted with D5W to a final volume of no more than 250 mL. If less than 250 mL is used, the concentration of prexasertib must be maintained within a range of 0.08 mg/mL - 1.6 mg/mL of prexasertib.

Reconstituted or diluted prexasertib should NOT be used if it appears turbid or contains foreign particles.

8.1.8 Administration

Prexasertib (LY2606368) should be administered IV over 1 hour (+/- 5 minute infusion window) using a central or free flowing peripheral IV line with an in-line, sterile, non-pyrogenic, 0.22- μ m filter. Reconstituted or diluted prexasertib should NOT be used if it appears turbid or contains foreign particles.

8.1.9 Ordering

Drug supply will be ordered from Eli Lilly by site pharmacy personnel.

8.1.10 Accountability

The investigator, or a responsible party designated by the investigator, should maintain a careful record of the inventory and disposition of the agent using the NCI Drug Accountability Record Form (DARF) or another comparable drug accountability form. (See the NCI Investigator's Handbook for Procedures for Drug Accountability and Storage.)

8.1.11 Destruction and Return

Expired supplies of prexasertib (LY2606368) should be destroyed according to institutional policies. Destruction will be documented in the Drug Accountability Record Form. At the end of the study, unused supplies of prexasertib should be destroyed according to institutional policies. Destruction will be documented in the Drug Accountability Record Form.

9. BIOMARKER, CORRELATIVE, AND SPECIAL STUDIES

9.1 Biomarker Studies

9.1.1 Exploratory Tumor Biopsy – Replicative Stress and HR Cohorts

Mandatory fresh tumor biopsies will be obtained from the patients enrolled to the replicative stress or HR cohorts during Stage 1 of the 2-stage trial. The biopsies will be obtained at baseline (any time prior to the first infusion).

Core biopsy samples should be obtained for analysis. Three-to-four biopsy passes utilizing a 16-18 gauge needle are preferable, but a 20 gauge core needle biopsy is also acceptable. Less than the goal amount of tissue is acceptable for the biopsy procedure, and should be based upon the clinical judgment of the treating investigator and the clinician performing the procedure.

Biopsy samples should be fresh frozen. A plastic cryomold should be labeled with the protocol number, study subject number, and the exact date and time of collection. Several drops of OCT compound will be placed into the cryomold and at time of biopsy the sample will be placed into OCT, covered with additional drops of OCT and then placed upon dry ice immediately. The specimen will then be stored at -80°C until used.

The frozen samples should be shipped to the Broad Institute Center for Cancer Precision Medicine. The baseline tumor tissue sample should be shipped at the same time as the germline blood sample as described below in **Section 9.1.3**.

Biopsy samples should be sent on dry ice to:

Broad Institute Center for Cancer Precision Medicine
[name]
ATTN: Samples Lab
[name]

9.1.2 Blood sample collection – All Cohorts

For **all** patients enrolling on trial, blood samples will be collected to be analyzed for cell-free DNA (cfDNA). A sample will be collected at baseline (prior to the first infusion), at visits immediately following restaging scans (i.e., cycle 3 day 1, cycle 5 day 1, cycle 7 day 1, etc.) and at the off study visit. Samples collected on days where a prexasertib infusion will be given can be collected anytime pre-infusion.

For the patients enrolling during Stage 1 of the trial in the replicative stress or HR cohorts **only**, a germline blood sample will be collected at baseline (any time prior to the first infusion) to be paired with the pre-treatment fresh tumor biopsy obtained for WES.

9.1.2.1 Germline Blood Sample for WES Collection Procedure (HR and Replicative Stress Cohorts):

Blood sample should be labeled with the protocol number, study subject number, and the date of

collection.

- One 10 mL sample will be drawn into an EDTA containing test tube.
- Freeze immediately upright at -80°C until shipping.
- **Both the germline blood sample and pre-treatment fresh tumor biopsy samples should be shipped to the Broad Institute at the same time for processing.**
- The samples should be sent to the following address to be processed:
Broad Institute Center for Cancer Precision Medicine
[name]
ATTN: Samples Lab
[name]

9.1.2.2 cfDNA Sample Collection Procedure (All Cohorts):

1. Draw two 9 mL blood samples into Streck Tubes.
2. Blood samples should be labeled with: cfDNA, protocol number, study subject number, and the date of the draw.
3. Within 2 hours of the draw time, cfDNA samples should be processed by the DF/HCC Clinical Trials Core laboratory as follows:
 1. Immediately centrifuge for 10 minutes at 1500 (+/- 150) x g. NOTE: Brake switch must be off so the cell/plasma interface is not disturbed.
 2. Pipette the plasma layer into a 15 mL tube labeled “CFDNA/with patient #”. Do not ship. NOTE: Do not dip the tip of the pipette into the plasma/cell interface. Leave a thin plasma layer intact over the interface.
 3. Centrifuge the 15 mL tube containing the plasma only for 10 minutes at 3000 (+/- 150) x g.
 4. Transfer using a fresh pipette, the supernatant into a second 15 mL tube labeled “CFDNA super.do not ship”. NOTE: Leave about 0.3 mL of supernatant in the centrifuged 15 mL tube. This leftover 0.3 mL contains cellular debris.
 5. Using a fresh pipette, transfer 1 mL of plasma from the “super.do not ship” tube into max four (4) 2 mL cryovials labeled CFDNA.ship.patient#/#
 6. Freeze immediately upright at -70°C or colder until shipping.
4. Samples should then be sent to the Broad Institute at:
Broad Institute of MIT and Harvard
[name]
[name]
[name]

10. STUDY CALENDAR

Baseline evaluations are to be conducted within 14 days prior to start of protocol therapy, with the exception of the informed consent and baseline tumor imaging which may be obtained up to 28 days prior to the start of protocol therapy. Assessments must be performed prior to

administration of any study agent.

	Table 10: Study Calendar								
	Screening ^a	Cycle 1 Day 1	Cycle 1 Day 8 ^b	Cycle 1 Day 15 ⁱ	Cycle 1 Day 22 ^h	Cycle 2+ Day 1 ⁱ	Cycle 2+ Day 15 ⁱ	Off Treatment ^k	Every 3 Months After Discontinuing ^l
Prexasertib (LY2606368)^b		X		X		X	X		
Informed consent	X								
Demographics	X								
Medical history	X								
Physical exam	X	X	X	X	X	X	X	X	
Vital signs^c	X	X	X	X	X	X	X	X	
Height	X								
Weight	X	X		X		X	X	X	
ECOG performance status	X	X		X		X	X	X	
CBC w/diff & Plt	X	X	X	X	X	X	X	X	
Serum chemistry^d	X	X	X	X	X	X	X	X	
β-HCG^e	X							X	
EKG^f	X	X				X			
Adverse Events		X	X	X	X	X	X	X	
Radiologic evaluation	X	CT or MRI imaging of any disease-involved site. Radiologic measurements should be performed at the end of cycle 2 (cycle 2 day 28) and at the end of every 2 cycles of treatment thereafter (i.e. cycle 4 day 28, cycle 6 day 28, and so on). There is a ± 7 day window on imaging evaluations.						X	
Fresh Tumor Biopsy^g	X								
Research Germline Blood Sample for	X								

Table 10: Study Calendar									
	Screening ^a	Cycle 1 Day 1	Cycle 1 Day 8 ^b	Cycle 1 Day 15 ⁱ	Cycle 1 Day 22 ^h	Cycle 2+ Day 1 ^j	Cycle 2+ Day 15 ⁱ	Off Treatment ^k	Every 3 Months After Discontinuing ^l
WES^g									
Research Blood Samples for cfDNA		X	cfDNA samples to be collected at the visit immediately following a restaging scan (i.e., cycle 3 day 1, cycle 5 day 1, cycle 7 day 1, and so on) as described in Section 9 .					X	
Telephone or Care Provider Contact									X

a) Screening evaluations are to be performed within 14 days of cycle 1 day 1, with the exception of the informed consent and baseline tumor imaging which may be obtained up to 28 days prior to cycle 1 day 1.
 b) Prexasertib (LY2606368) dose as assigned; see administration guidelines in **Section 5**.
 c) Heart rate, respiratory rate, blood pressure, temperature, and oxygen saturation (O₂ sat). On infusion days, vital signs are to be collected anytime pre-infusion (exact time of vital signs should be recorded). May be repeated as clinically indicated.
 d) Sodium, potassium, chloride, CO₂, blood urea nitrogen (BUN), creatinine, glucose, albumin, total protein, alkaline phosphatase, total bilirubin, SGOT [AST], SGPT [ALT], globulin, and magnesium. Other tests may be ordered as clinically indicated.
 e) Serum pregnancy test only required for women of childbearing potential. Childbearing potential defined as any female who has experienced menarche and who has not undergone successful surgical sterilization (hysterectomy, bilateral tubal ligation or bilateral oophorectomy) or is not postmenopausal (defined as amenorrhea >12 consecutive months; or women with a documented plasma follicle-stimulating hormone level >35μIU/mL).
 f) To be performed at screening, at any time pre-dose on cycle 1 day 1, upon completion of the first infusion (+15 minute window from the end of the infusion), and 1 hour after the end of the infusion (+30 minute window). EKG to be completed pre-dose (any time prior to the infusion) on the first day of each subsequent cycle. Additional EKGs may be performed as clinically indicated at the treating investigator's discretion. If QTcF increases > 30 msec from screening EKG at any time point, EKG should be repeated at 10 minutes after the end of the infusion (± 5 minute window), 30 minutes after the end of the infusion (± 10 minute window), and 1 hour after the end of the infusion (+30 minute window). The exact time of all EKGs should be recorded.
 g) Baseline fresh tumor biopsy and germline blood sample for WES required for the patients enrolled during Stage 1 of the HR and replicative stress cohorts. Please see **Section 9** for further detail.
 h) Cycle 1 day 8 and cycle 1 day 22 may be shifted by ± 3 days for scheduling issues (vacations, holidays, adverse weather, etc.).
 i) Day 15 assessments and infusion may shifted ± 1 day for scheduling issues (vacations, holidays, adverse weather, etc.).
 j) The start of a subsequent cycle may be delayed by up to 7 days for scheduling issues (vacations, holidays, adverse weather, etc.).
 k) Off-treatment evaluation. Note: follow up visits or other contact is required in order to identify SAEs during the 30 days following the end of study treatment.
 l) Participants will be followed until death or withdrawal of consent after removal from protocol therapy for survival status only. This follow up will be performed by review of the medical record, contact with care providers, and/or telephone contact as needed every 3 to 4 months.

11. MEASUREMENT OF EFFECT

11.1 Antitumor Effect

For the purposes of this study, participants should be re-evaluated for response at the end of every 2 cycles of treatment (every 8 weeks) as described in the **Study Calendar**. In addition to a baseline scan, confirmatory scans should also be obtained not less than 4 weeks following initial documentation of objective response.

Response and progression will be evaluated in this study using the new international criteria proposed by the Response Evaluation Criteria in Solid Tumors (RECIST) guideline (version 1.1) [*Eur J Ca* 45:228-247, 2009]. Changes in the largest diameter (unidimensional measurement) of the tumor lesions and the shortest diameter in the case of malignant lymph nodes are used in the RECIST criteria.

11.1.1 Definitions

Evaluable for Target Disease response. Only those participants who have measurable disease present at baseline, have received at least one cycle of therapy, and have had their disease re-evaluated will be considered evaluable for target disease response. These participants will have their response classified according to the definitions stated below. (Note: Participants who exhibit objective disease progression prior to the end of cycle 1 will also be considered evaluable.)

Evaluable Non-Target Disease Response. Participants who have lesions present at baseline that are evaluable but do not meet the definitions of measurable disease, have received at least one cycle of therapy, and have had their disease re-evaluated will be considered evaluable for non-target disease. The response assessment is based on the presence, absence, or unequivocal progression of the lesions.

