13. STATISTICAL CONSIDERATIONS

This is a three-arm phase II study exploring the anti-tumor activity of prexasertib (LY2606368) in patients with advanced cancer exhibiting either replicative stress, HR deficiency, or *CCNE1* amplification. The primary goal of the study will be to examine the progression-free rate at 4 months in all arms separately. Secondary efficacy measures will include assessment of objective response rate by RECIST 1.1 as well as toxicity using CTCAE version 4.0 criteria, overall survival (OS), and progression free survival (PFS).

Each arm will be conducted as a Simon's 2-stage design and will initially enroll 9 participants. If there are less than 2 subjects that are alive and progression-free at 4 months after initiation of prexasertib, that arm will be terminated. If 2 or more subjects are progression free by 4 months, then enrollment for that arm will be expanded to 19 subjects. A minimum of 6 patients must be alive and progression-free at 4 months for the cohort to be considered meaningful for further evaluation. If at any point a participant does not complete Cycle 1 dosing of the study agent, that participant may be replaced at the principal investigator's discretion.

Progression status by 4 months will be determined for all patients. We expect all patients to have this status documented. PFS will be defined as the time from study registration to documented disease progression per RECIST 1.1 criteria or death from any cause, whichever occurs first. OS will be defined as the time from study registration until death. Patients who have not experienced an event of interest by the time of analysis will be censored at the date they are last known to be progression-free for PFS and alive for OS.

This design provides 80% power to detect a progression-free rate at 4 months of 40% tested against a historical control rate of $\leq 15\%$ ⁵⁷ using a one-sided significance of 0.05.

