13.3 Analysis of Primary and Secondary Endpoints

The primary and secondary analyses will include all eligible patients who completed at least one cycle of dosing. The exception to this includes the planned analysis of toxicity data, which will include all patients who received study drug regardless of eligibility and regardless of whether they completed a full cycle. Progression-free rate will be estimated as binomial proportion and overall survival and progression-free survival estimates and curves will be generated using the Kaplan-Meier method.

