13.5.2 Evaluation of the Primary Efficacy Endpoint

All eligible participants included in the study who complete at least one cycle of dosing will be assessed for response, even if there are major protocol therapy deviations. Each participant should be assigned one of the following categories: 1) complete response, 2) partial response, 3) stable disease, 4) progressive disease, 5) early death from malignant disease, 6) early death from toxicity, 7) early death because of other cause, or 9) unknown (not assessable, insufficient data). By arbitrary convention, category 9 usually designates the "unknown" status of any type of data in a clinical database.

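### Section 11.1.1 and Sections 13.3/13.5.2 define different sets for response, and nothing says which one is the ORR denominator

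*Combined protocol and SAP*

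**What the plan says.** ORR is a secondary endpoint. Section 13 states: "Secondary efficacy measures will include assessment of objective response rate by RECIST 1.1". Three places bear on who enters it.

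- **Section 11.1.1 (Definitions).** Of participants with measurable disease at baseline, only those who "have received at least one cycle of therapy, and have had their disease re-evaluated will be considered evaluable for target disease response". A note widens this: "Participants who exhibit objective disease progression prior to the end of cycle 1 will also be considered evaluable".
- **Section 13.3.** "The primary and secondary analyses will include all eligible patients who completed at least one cycle of dosing". One departure is stated: "The exception to this includes the planned analysis of toxicity data". There is none for response.
- **Section 13.5.2.** "All eligible participants included in the study who complete at least one cycle of dosing will be assessed for response". Each is given a category. The list includes three kinds of early death and ends "or 9) unknown (not assessable, insufficient data"). The section is headed as the primary endpoint, but its text is about response.

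On timing, Section 11.1 says that "participants should be re-evaluated for response at the end of every 2 cycles of treatment (every 8 weeks").

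**The concern.** An analyst could follow Section 11 or Section 13, report a different ORR from the same data, and claim to have followed the protocol either way.

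The re-evaluation condition deserves particular attention. A participant with no post-baseline evaluation has no documented response. Removing that participant shrinks the denominator and never the numerator, so when the condition is applied it can only raise ORR (or leave it at zero if nobody responds). The completed-cycle condition in 13.3 and 13.5.2 does the same to participants with objective progression during cycle 1. Each rule therefore leaves out a group of non-responders that the other keeps. With at most 19 participants per arm, one or two people move the reported rate visibly.

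**Working it through.** **1. The plan's own figure.** No target, power or precision is given for ORR. The only design figure is for 4-month progression-free status (Section 13): 9 participants, continue if at least 2 succeed, 19 in total, success if at least 6, with rates of 15% and 40%.

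P(success) = sum over x = 2 to 9 of C(9,x) p^x (1−p)^(9−x) × P(Bin(10,p) ≥ 6−x)

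- p = 0.15: 0.0497, against a stated one-sided 0.05.
- p = 0.40: 0.8132, against a stated 80%.

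The design reproduces. Its decision rule does not use tumour response, so the conflict over ORR does not touch it.

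**2. The sets side by side, for eligible participants.**

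| Participant | 11.1.1 | 13.3 and 13.5.2 |
|---|---|---|
| Completes cycle 1, re-evaluated | in | in |
| Completes cycle 1, no post-baseline evaluation | out | in (early death or unknown) |
| Objective progression, cycle 1 not completed | in | out |
| Stops or dies in cycle 1 without objective progression, cycle not completed | out | out |

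Rows two and three are the conflict. Row four shows that choosing between the existing rules does not recover every early failure. Measurable disease is an entry criterion (3.1.3), so that part of 11.1.1 changes nothing here. Section 11.1.1 has no eligibility condition, which is a further small mismatch.

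**3. When row two can arise.** A cycle is 28 days (5.1), and scheduled imaging falls at the end of cycle 2, ±7 days (Table 10). About 56 − 28 = 28 days lie between completing cycle 1 and the first scheduled scan.

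**4. Size, with assumed counts.** Let x be the number of responders, 19 the number of eligible completers, d the completers never re-evaluated, and e the objective progressors who did not complete cycle 1. The documents give none of x, d or e.

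- ORR under 13.3/13.5.2 = x/19
- ORR under 11.1.1 = x/(19 − d + e)

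With x = 4:

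- 13.3/13.5.2: 4/19 = 21.1% (exact 95% interval 6.1% to 45.6%).
- 11.1.1, e = 0, d = 1, 2, 3, 4: 4/18 = 22.2%, 4/17 = 23.5%, 4/16 = 25.0%, 4/15 = 26.7%.
- 11.1.1, d = 0, e = 1: 4/20 = 20.0%.
- 11.1.1, d = e: 4/19 = 21.1%, the same rate from different participants.

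With x = 3, d from 0 to 4 and e from 0 to 3, the 11.1.1 rate runs from 3/22 = 13.6% to 3/15 = 20.0%, against 3/19 = 15.8% under 13.3/13.5.2.

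The replicative stress arm closed with 10 enrolled (13.2), so a denominator of 19 illustrates only an arm that expands fully.

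**The case against.** The best reply is that there is no real conflict. Section 11.1.1 describes who can be classified by RECIST and never mentions ORR, a rate or an analysis set. Section 13.3 does set the population for secondary analyses and makes an exception only for toxicity. Section 13.5.2 then keeps unscanned completers through its early-death and unknown categories. On that reading 13.3 governs and the upward bias never arises.

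This is a reasonable reading, but the plan does not state it. ORR is to be assessed by RECIST 1.1, Section 11 is where the protocol sets out RECIST evaluation, and its wording there is restrictive. If 13.3 is meant to govern, one sentence would settle it. That reading also still leaves out cycle 1 progressors whom 11.1.1 expressly keeps.

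Other parts of the reply stand:

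- A reader might infer that 11.1.1 drops everyone who fails before the first scheduled scan. It does not. Its note keeps objective progressors in cycle 1, Table 10 lists imaging at the off-treatment visit, and Section 11.1.3.4 asks for every effort to document progression after discontinuation. Only participants with no post-baseline evaluation at all are lost.
- A reader might infer that 11.1.1 inflates ORR overall relative to 13.3. The documents do not support that either: the note adds non-responders, and the net sign depends on d and e.
- Every shift shown is small against the sampling error of 19 participants.
- ORR has no test and no go/no-go role.

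**Conclusion.** The point holds as an unreconciled definition for a secondary endpoint. Sections 11.1.1 and 13.3/13.5.2 differ in both directions, and nothing ranks them. Each rule leaves out non-responders that the other counts. The difference between them can therefore take either sign: with 4 assumed responders among 19 completers, 20.0% to 26.7% in the cases shown, against 21.1%. The contradiction rests on the text alone; the size rests on assumed counts. The 9/19/6 design and the primary endpoint's operating characteristics are unaffected. It is worth correcting because the correction is nearly free and the re-evaluation condition, when applied, can only favour the drug.

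**What to change.** State one ORR denominator, in the same words, in Sections 11.1.1, 13.3 and 13.5.2:

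- Remove disease re-evaluation as a condition for the ORR denominator. It may stay as a description of who can be classified by RECIST.
- Keep participants with objective progression in cycle 1 in the denominator.
- State that early progression, early death and unknown or not assessable count as non-response.

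The least biased set is all eligible participants who received at least one dose. This goes further than reconciling the three sections, since none of them uses that set for response, but it also recovers those who stop or die in cycle 1 without objective progression. Section 13 lets the principal investigator replace participants who do not complete cycle 1, so the text must say that replaced participants stay in the ORR denominator.

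At a minimum, add a sentence that the 13.3 set governs ORR. That removes the ambiguity but leaves cycle 1 non-completers out.

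The cost is wording, a slightly less favourable ORR, and an ORR denominator that may differ from that of the primary endpoint unless 13.3 is aligned.
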